3.10 Criteria for withdrawal

Participants may be prematurely terminated from the study for the following reasons:

- 1. The participant elects to withdraw consent from all future study activities, including follow-up.
- 2. Participant develops severe complications from their EoE/EGE (for instance, esophageal strictures).
- 3. Participant required EGID rescue medicines that the investigator feels are substantial.
- 4. Participant becomes pregnant.
- 5. The participant is "lost to follow-up" (i.e., no further follow-up is possible because attempts to reestablish contact with the participant have failed).
- 6. The participant develops an SAE related to therapy.
- 7. The participant dies.
- 8. The Investigator no longer believes participation is in the best interest of the participant.

Enrolled participants who start on the initial intervention protocol and prematurely discontinue/withdraw from the study will be replaced if they do not reach the End of Treatment (V5) visit of the study, including the EGD. Additional participants will be enrolled in the same manner as all other participants. Participant numbers will not be re-used. All enrolled participants will be included into intent to treat analysis.

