3.10.2 Withdrawal of the informed consent

Subjects may choose to withdraw consent at any time during study participation. When a participant withdraws permission, they will no longer be part of the study and no new information about the subject will be gathered for the study except for information related to an adverse event that is related or potentially related to the study.

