3.10.3 Early withdrawal

Subjects may be asked to complete an EOT/Early withdrawal visit prior to withdrawal per the discretion of the PI.

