4.2 Treatment period

Visit 2 (Baseline Week 0)

- Administer study drug
- Inclusion/Exclusion
- Randomization
- Concomitant medications/procedures
- GI symptoms and pain interference
- PROs (EESAI, EoE-QOL-A, SODA, PedsQL, PEESS, PROMIS)
- Vital Signs, Weight
- Diet Questionnaire
- Adverse Events
- Pregnancy Testing: urine
- Research samples (whole blood/serum/plasma)

Visit 3 (Week 4)

- Administer study drug
- Concomitant medications/procedures
- GI symptoms and pain interference
- PROs (EESAI, EoE-QOL-A, SODA, PedsQL, PEESS, PROMIS)
- Vital Signs, Weight
- Adverse Events
- Pregnancy Testing: urine
- Clinical labs (hematology and serum chemistry, urinalysis)
- Research samples (whole blood/serum/plasma)

Visit 4 (week 8)†

- Administer study drug
- Concomitant medications/procedures
- GI symptoms and pain interference
- PROs (EESAI, EoE-QOL-A, SODA, PedsQL, PEESS, PROMIS)
- Vital signs, weight
- Adverse Events
- Pregnancy Testing: urine
- Research samples (whole blood/serum/plasma)

[†] This visit may be repeated until an EGD can be performed for participants whose EGDs are postponed due to COVID-19. Participants may have study drug administered by their local providers due to COVID-19 travel restrictions and travel risks. In these cases, adverse events and concomitant meds will be assessed by study team via telephone/telemedicine prior to the visit to local provider. Pregancy testing and vitals will occur by local provider or local lab per PI discretion. Results from testing will be provided to the study staff directly from the local provider (via medical record release when necessary). Date and time of study drug injection and post injection monitoring results will also be provided to study staff from the local provider.

Visit 5 (Week 12 - End of Treatment/Early Withdrawal)

- Concomitant medications/procedures
- GI symptoms and pain interference
- PROs (EESAI, EoE-QOL-A, SODA, PedsQL, PEESS, PROMIS)
- Physical Exam, Vital Signs, Weight
- Diet Questionnaire
- Adverse Events

- Pregnancy Testing: urine
- Endoscopy with biopsies
- Endoscopic and Histologic metrics (EREFS, HSS, Lanza score, EG Biopsy Evaluation Form, ED Biopsy Evaluation Form)
- Clinical labs (hematology and serum chemistry, urinalysis, pregnancy testing, IgE)
- Research samples (whole blood/serum, plasma, stool microbiome)

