8.3 Definitions of analysis sets

8.3.1 Efficacy analysis set

There will be one efficacy analysis set. That is the intention-to-treat (ITT) set. This comprises all enrolled patients who took at least one dose of study medication.

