8.4 Outcome measures for analyses

The primary efficacy endpoints are the eosinophil count response rate to the treatments. A disease remission is defined by peak eosinophil counts less than 15 for esophagus, less than 30 for stomach, and less than 52 for duodenum. A patient is considered in remission if all applicable counts are in remission range. The rate of remission among all patients is the primary efficacy measure for both treatment groups.

Secondary outcome measures include individual disease remission rate, changes in endoscopic scores from pre to post-treatment as measured by EREFS for EoE and Lanza score for EGE, changes in histologic scores from pre to post-treatment, changes in blood eosinophil count pre and post-treatment, changes in symptom scores from pre to post-treatment measured by EESAI, EoE-QoL-A (for EoE), and SODA (for EGE), and changes in peak eosinophil counts in biospies from pre to post-treatment.

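### Section 8.4 scores remission on eosinophil counts alone, so in-range counts obtained after EGID rescue would be credited to the assigned arm

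*Combined protocol and SAP*

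**What the plan says.** **Scoring.** Section 8.4 sets a peak-count threshold for each gut segment and then states: "A patient is considered in remission if all applicable counts are in remission range". It adds: "The rate of remission among all patients is the primary efficacy measure for both treatment groups". Section 2.1 defines the primary outcome on the stomach alone, but also by count alone. Section 8.5.1 names Fisher's exact test and says nothing about rescue.

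**Who is analysed.** Section 3.10 says: "All enrolled participants will be included into intent to treat analysis". Section 8.3.1 defines the efficacy set as ITT: "This comprises all enrolled patients who took at least one dose of study medication". Neither requires an end-of-treatment EGD. Section 3.10 also replaces patients who do not reach the Visit 5 EGD.

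**When biopsies are taken.** Section 4.2 labels the visit "Visit 5 (Week 12 - End of Treatment/Early Withdrawal)" and lists endoscopy with biopsies under it. Section 3.10.3 makes attendance on withdrawal optional: "Subjects may be asked to complete an EOT/Early withdrawal visit prior to withdrawal per the discretion of the PI". If consent is withdrawn, 3.10.2 says that "they will no longer be part of the study and no new information about the subject will be gathered for the study", apart from certain adverse-event information.

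**Rescue.** Section 7.7 does not permit rescue for EGID flares and says that it results in withdrawal. Section 3.10 lists, among reasons for which a participant may be terminated: "Participant required EGID rescue medicines that the investigator feels are substantial". Both rules concern participation. Neither says how the outcome is scored.

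**Sensitivity.** Section 8.5.5 offers logistic regression with covariates such as gender, age and baseline count. Section 8.5.3 mentions a per-protocol analysis but does not define its population.

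**The concern.** The primary objective is to compare benralizumab with placebo. If a patient needs rescue for the disease under study and the later biopsy is in range, a counts-only rule credits the rescue to whichever arm the patient was assigned to.

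Two routes lead to such a biopsy. A patient withdrawn for rescue may be asked to attend the early-withdrawal visit, which is Visit 5 and includes the EGD. Alternatively, under 3.10, a patient whose rescue is not judged substantial may remain and reach Visit 5 in the ordinary way. Withdrawn patients stay in the ITT analysis, so either biopsy can feed the primary rate.

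In-range counts after rescue are plausible. Section 1.1 describes current treatment, including swallowed topical corticosteroids, as effective while it is continued. How often rescue would bring every applicable segment into range is not stated.

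The error can run either way. A rescued active patient scored as a remission favours benralizumab; a rescued placebo patient scored as a remission favours placebo. With 12 or 13 patients per arm, one such patient can decide a borderline result, and a scoring decision made without a written rule is open to challenge.

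**Working it through.** **Inputs from section 8.2.** Remission 70% on benralizumab and 10% on placebo; two-sided Fisher's exact test at 0.05; 12 completers per arm; 26 enrolled, which is 13 per arm under 1:1 allocation. **Assumed:** the number of rescued patients (one or two), since the documents give no rate.

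**Formula.** Power = Σₐ Σᵦ Bin(a; n₁, 0.70) × Bin(b; n₂, 0.10) × 1{Fisher p < 0.05}, summed over all tables. A rescued patient is taken out of the binomial part and added back as a fixed 0 (not in remission) or a fixed 1 (remission).

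**Step 1: the plan's own figure.** 11 per arm gives 75.5% and 12 per arm gives 82.6%, so 12 per arm for 80% power reproduces. 13 per arm gives 88.0%.

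**Step 2: rescue and p-values near the boundary (12 per arm).**

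| Scored as not in remission | p | Scored as remission | p |
|---|---|---|---|
| 6/12 v 1/12 (one rescued, active) | 0.069 | 7/12 v 1/12 | 0.027 |
| 8/12 v 1/12 (one rescued, placebo) | 0.009 | 8/12 v 2/12 | 0.036 |
| 8/12 v 1/12 (two rescued, placebo) | 0.009 | 8/12 v 3/12 | 0.100 |

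The last two rows start near the planned effect (12 × 0.70 = 8.4 and 12 × 0.10 = 1.2). One rescued placebo patient leaves the result significant; two do not.

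**Step 3: rescue and power (70% v 10%, 13 per arm).**

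| Rescued patients | Not in remission | In range half the time | Remission |
|---|---|---|---|
| One, placebo | 89.2% | 83.1% | 77.0% |
| One, active | 80.9% | 86.0% | 91.0% |
| One in each arm | 82.6% | not calculated | 81.8% |

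The middle column is the mean of the outer two. One rescued placebo patient scored as a remission costs 89.2 − 77.0 = 12.2 points. One rescued active patient adds 91.0 − 80.9 = 10.1 points of apparent power, which rescue earned rather than benralizumab. With one in each arm the difference is 82.6 − 81.8 = 0.8 points.

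**Step 4: no EGD.** The denominator is all patients, and a patient without biopsies cannot be shown to be in range, so the text already leads to non-remission. From 8/12 v 2/12 (p=0.036), two patients without an EGD in each arm give 8/14 v 2/14, p=0.046, still significant. Only an imbalance, two on active and none on placebo, crosses the line (8/14 v 2/12, p=0.051).

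**Step 5: power if affected patients are counted as failures.** With replacement to 12 completers per arm plus two failures per arm (14 per arm), power is 80.2%. At 13 per arm without replacement, one failure per arm gives 82.6% and two give 75.5%.

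**The case against.** The strongest reply is that 7.7 largely closes the route: rescue means withdrawal, and a withdrawn patient supplies counts only if the investigator asks for the optional visit. The second route exists only because 3.10 is softer than 7.7. This stands as a limit on frequency, but the contradiction is in the current text and leaves the route open.

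Scoring Week 12 counts regardless of rescue is also a recognised treatment-policy approach, and the wording of 8.4 is compatible with it. If rescue is commoner on placebo, that approach is conservative for benralizumab. This is fair, but the plan nowhere says the choice was made. The proposed fix keeps that analysis as a sensitivity analysis.

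Third, plausibility is limited. Section 3.1 recruits patients with active gastric disease who are symptomatic despite treatment, corticosteroids among the examples, so rescue may often fail to normalise counts. The documents cannot settle this, and confidence is lowered accordingly.

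Two stronger readings are tempting. A reader might infer that the primary result is biased towards benralizumab. The documents do not support this: the direction depends on which arm the rescued patient is in, and balanced rescue is nearly neutral. A reader might also infer that patients without an EGD have no defined outcome or would be dropped. Sizing on completers and replacing patients who miss the EGD give that some colour, but the ITT set and the all-patients denominator point to non-remission. The per-protocol analysis in 8.5.3 does not test that assumption, since its population is undefined.

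**Conclusion.** The point holds for rescue: as written, 8.4 credits in-range counts after EGID rescue to the assigned arm. The route is narrow and its frequency unknown. In the illustrations, a single patient can move a borderline p-value across 0.05, or shift power by about 10 to 12 points; balanced rescue changes little.

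This rests on three assumptions: that at least one rescued patient is biopsied at Visit 5, that the counts are then in range, and that the dual label of Visit 5 makes an early-withdrawal biopsy a source of endpoint counts. It holds whether the endpoint is stomach only (2.1) or all applicable segments (8.4).

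For a missing EGD, only an explicit sentence is lacking. The sample size is sound on its own inputs. The change should be made; the gap does not make the trial uninterpretable. Confidence is moderate.

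**What to change.** 1. **Section 8.4:** state that an ITT patient who received EGID rescue before the end-of-treatment EGD is counted as not in remission in the primary analysis.
2. **Section 8.5.5:** add a sensitivity analysis of the primary endpoint that scores counts regardless of rescue.
3. **Sections 7.7 and 3.10:** reconcile the two statements on rescue, so that the scoring rule uses one definition. Which clinical rule applies is for the sponsor to decide.
4. **Clarification only, section 8.4:** write down that an ITT patient with no end-of-treatment EGD is not in remission. A best/worst-case or tipping-point check by arm is optional.

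The cost is wording and one further analysis, with no new visits or samples. The downside is that patients who leave for reasons unrelated to efficacy count as failures. With replacement as 3.10 provides, two per arm still leave power at 80.2%; the 75.5% figure applies only without replacement. The wording should be settled before treatment codes are released for analysis.

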8.5 Methods for statistical analyses

8.5.1 Analysis of the primary variable(s)

The comparison of primary response/remission rates between the benralizumab and placebo groups will be made with a Fisher's exact test of binomial distributions.

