8. STATISTICAL ANALYSES

8.1 Statistical considerations

Pertaining to the primary objective of this study, the primary efficacy endpoint is the eosinophil count response rate to the treatments. The comparison of response rates between the benralizumab and placebo groups will be made with a Fisher's exact test of binomial distributions. For secondary endpoints, continuous variables comparisons between the two groups, e.g. change in peak eos counts, change in blood eosinophil count, change in symptom scores from pre- to post-treatment, and change in endoscopic scores from pre- to post-treatment at each study visit (e.g. Weeks 4, 8 and the end of treatment) will be made in a repeated measure ANOVA model, where serial correlation within patients will be accounted for. Proper transformation of data, e.g. logarithmic, or non-parametric methods may be applied to satisfy statistical assumptions. Categorical responses, e.g. response rate will also be compared using a Fisher's exact test, by visit if applicable. Additional exploratory analysis to investigate other

factors' effect on response may also be performed, with generalized linear models with appropriate link functions.

All comparisons are two-sided, and p-value < 0.05 is considered statistically significant. No multiplicity adjustment will be made for this analysis.

Safety measurements, including adverse events will be summarized by descriptive statistics. The total numbers of AE's as well as number of patients with an AE will be summarized via N and percent.

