8.2 Sample size estimate

The planned total sample size of 24 subjects is justified based on previously published studies. Based on trials of other therapies in EoE and EGID, it is reasonable to assume that an eosinophil count at or below 15, 30 and 52 eos/hpf in esophagus, stomach and duodenum, respectively, after treatment, is considered an adequate response. It is estimated that in the placebo group, the response rate will be no more than 10%. We assume that the benralizumab group response rate will be about 70%. To detect a difference between these two response rates, we need a total of 24 completed subjects, or 12 subjects per arm to reach 80% statistical power. This is based on a two-sided Fisher's exact test at 0.05 level. We will enroll 26 subjects to account for possible dropouts.

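### Cheap improvement, not an error: with the same patients, Boschloo's exact test adds about 7 points of power to the primary comparison at 12 per arm and about 4 at 13 per arm

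*Combined protocol and SAP*

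**What the plan says.** The primary analysis is set out in section 8.5.1: "The comparison of primary response/remission rates between the benralizumab and placebo groups will be made with a" Fisher's "exact test of binomial distributions". Section 8.1 gives the decision rule: "All comparisons are two-sided, and p-value < 0.05 is considered statistically significant".

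Section 8.2 bases the sample size on the same procedure, a two-sided Fisher's "exact test at 0.05 level", and arrives at "12 subjects per arm to reach 80% statistical power". The rates behind it are "It is estimated that in the placebo group, the response rate will be no more than 10" per cent and "We assume that the benralizumab group response rate will be about 70" per cent. Enrolment is 26, to allow for dropouts.

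Three other sections bear on the point:
- Section 3.5 allocates 1:1.
- Section 8.3.1 defines one efficacy set, namely everyone enrolled who received at least one dose, so the analysed arms need not be 12 and 12.
- Section 8.5.4 plans no interim analysis, so the whole 0.05 is available to the final test.

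The documents do not discuss the test's attained size or any unconditional alternative.

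**The concern.** The design fixes the two arm sizes. Fisher's test conditions, in addition, on the total number of responders, which the design leaves free. With arms this small only a few p-values are possible for each total, and the test often cannot come close to spending 0.05. The unspent error is power forgone.

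In a trial with 24 planned completers this is visible. Results such as 6/12 v 1/12 or 7/12 v 2/12 would be declared non-significant, although an exact test exists that rejects them and still holds the 5% level. The loss is larger if benralizumab does less well than the assumed 70%.

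**Working it through.** **Inputs.** Two-sided test, significant if p < 0.05 (8.1); rates 70% and 10%, and 12 completers per arm (8.2); 26 enrolled at 1:1 (8.2, 3.5), so 13 v 13 if all are dosed and analysed (8.3.1).

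**Formulas.** Let *a* of n₁ benralizumab and *b* of n₂ placebo patients respond, as independent binomials.
- Power = Σ P(a; n₁, 0.70) × P(b; n₂, 0.10), summed over the tables that the test rejects.
- Size = the maximum over a common rate p of the same sum with p in both arms (grid of 1,999 values of p).
- Boschloo: order the tables by two-sided Fisher p-value and enlarge the rejection region for as long as size stays at or below 0.05.

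**Step 1: the plan's own figure.** Fisher's power is 75.5% at 11 per arm and 82.6% at 12 per arm. Twelve is therefore the smallest equal arm size that reaches 80%, and N = 24 reproduces.

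**Step 2: both tests at 12 v 12.** For each placebo count, the smallest benralizumab count that rejects, the chance of reaching it at 70%, and the contribution to power:

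| b | P(b) at 10% | Fisher needs a ≥ | P at 70% | product | Boschloo needs a ≥ | P at 70% | product |
|---|---|---|---|---|---|---|---|
| 0 | 0.2824 | 5 | 0.9905 | 0.2798 | 4 | 0.9983 | 0.2820 |
| 1 | 0.3766 | 7 | 0.8822 | 0.3322 | 6 | 0.9614 | 0.3620 |
| 2 | 0.2301 | 8 | 0.7237 | 0.1665 | 7 | 0.8822 | 0.2030 |
| 3 | 0.0852 | 9 | 0.4925 | 0.0420 | 9 | 0.4925 | 0.0420 |
| 4 | 0.0213 | 10 | 0.2528 | 0.0054 | 10 | 0.2528 | 0.0054 |
| 5 | 0.0038 | 11 | 0.0850 | 0.0003 | 10 | 0.2528 | 0.0010 |
| Sum | | | | **0.826** | | | **0.895** |

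Rows with b ≥ 6, and rejections in favour of placebo, add nothing at this precision. The gain is 89.5 − 82.6 = 6.9 points.

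The boundary can be checked by hand. For 4/12 v 0/12 the two-sided Fisher p is 2 × C(12,4)/C(24,4) = 2 × 495/10,626 = 0.093. For 5/12 v 0/12 it is 2 × 792/42,504 = 0.037. Fisher's p is 0.069 for 6/12 v 1/12 and 0.089 for 7/12 v 2/12. Boschloo rejects at Fisher p ≤ 0.0932, so it adds 4–0, 6–1, 7–2, 10–5, 11–6 and 12–8 with their mirror images, and loses no table.

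**Step 3: size at 12 v 12.** Fisher: maximum 2.28% (at a common rate of 50%), and 0.25% if both rates are 10%. Boschloo: maximum 4.49%. Barnard's test, with pooled or unpooled Z, gives the same rejection region as Boschloo here.

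**Step 4: other arm sizes** (benralizumab v placebo, placebo rate 10%):

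| Arms | Fisher max. size | Power at 70%: Fisher → Boschloo | Gain at 70% | Gain at 60% |
|---|---|---|---|---|
| 12 v 12 | 2.3% | 82.6% → 89.5% | 6.9 | 13.1 |
| 13 v 13 | 2.9% | 88.0% → 92.2% | 4.2 | about 10 |
| 13 v 12 | 4.3% | 89.2% → 90.9% | 1.7 | about 5 |
| 12 v 13 | 4.3% | 91.0% → 92.1% | 1.1 | about 4 |

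At 60% v 10% and 12 v 12 the powers are 63.9% and 77.0%; at 50% v 10% they are 42.5% and 58.8%. Boschloo's size stayed below 5% in every split, and its region always contained Fisher's.

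**The case against.** The strongest reply is that nothing here is wrong. The test in 8.5.1 is the test used for sizing in 8.2, it controls the type I error, and it delivers slightly more than the power promised. Conditional against unconditional exact inference is a recognised choice on which statisticians differ. All of that stands.

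A reader might infer from the 2.3% that the test misses a promised 5% level. The documents do not support this: 8.1 sets a significance threshold and nowhere claims an attained size of 5%.

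A reader might also infer that the trial gives up 7 points of power, or that changing the test is worth more than one or two extra patients per arm. Both depend on exactly 12 v 12, and 8.3.1 does not make 12 completers per arm the analysis set. Section 3.10 replaces early dropouts yet keeps everyone enrolled in the intention-to-treat analysis, and section 3.3 speaks of a minimum of 26, so arms of 13, larger arms or slightly unequal arms are all plausible. One more placebo patient alone (12 v 13) takes Fisher to 91.0%, above Boschloo at 12 v 12. Much of the conservatism comes from the discreteness of small equal arms and largely disappears when they differ by one.

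Finally, the protocol is at Edition 8. A late switch to a test under which 4/12 v 0/12 is significant will draw questions even if it is made while still blinded. That is a fair cost, and the reason to keep Fisher's result on display.

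**Conclusion.** This is an optional efficiency gain. The planned analysis is sound as written.

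At 70% v 10%, Boschloo's test adds 6.9 points of power at 12 v 12, 4.2 points at 13 v 13 (the split if all 26 are dosed and analysed), and about 1 to 2 points when the arms are 13 and 12. At 60% v 10% the corresponding gains are about 13, 10 and 4 to 5 points. Power cannot fall: Fisher's own size never exceeds 5%, so Boschloo's region always contains Fisher's.

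The figures assume independent binomial responses and the planned rates in everyone analysed. If non-completers are counted as non-responders, the rate in the 13 v 13 row would be below 70%, and the 60% column is then the better guide. Section 2.1 defines remission by the stomach alone, whereas 8.4 requires all applicable segments. The calculation does not settle that difference, and it enters here only through the rates. The recovered test has a size of about 4.5% to 4.9% in the splits tabulated, so it does not use the full 5% either.

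**What to change.** Before unblinding, amend 8.1 and 8.5.1 to name Boschloo's exact test as the primary test: two-sided, 0.05, with the two-sided Fisher p-value as its statistic, and the software and version stated. The definition needs to be explicit. The variants tried agree at 12 v 12 and 13 v 13 but reject slightly different tables when the arms are unequal. Report Fisher's exact test as a sensitivity analysis in 8.5.5.

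Keep the sample size. In 8.2, either leave 80% as a minimum or quote power by arm size (89.5% at 12 v 12, 92.2% at 13 v 13, for 70% v 10%). A single figure of 89% would be wrong for any other split.

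The cost is amendment wording and a short programming check; no patient, visit or procedure changes. The drawback is that the test is less familiar and some readers prefer conditional inference, which showing Fisher alongside addresses. If the blind has already been broken, leave Fisher's test as primary.
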